2.0 (25-Oct-2021)	Amendment 3 (04-Oct-2021)	
 • Definition of ITT analysis set changed to match that in the protocol • Update to hypothetical estimand to detail key inclusion/exclusion criteria that lead to exclusion from population • Details of planned and ad hoc interim analyses added • Removal of 250mg IM dose from analyses and testing hierarchy • Region and vaccination status removed as covariates from analysis models, and the 12-17 years and 18-64 years age groupings combined in the age group covariate. • Methods for imputing COVID-19 progression status and viral load data corrected and clarified • Details added for cut-point used to define persistently high viral load • Inclusion of long COVID exploratory endpoint • Amend Week 24 timepoint to Week 36 due to increased length of follow-up in the study 	
Clarifications made to language in SAP to better align to language used in protocol amendments.
 
250mg IM arm removed from analyses and testing hierarchy due to being permanently discontinued from study at ad hoc interim analysis.
 
Model covariates amended due to small numbers of patients in non-US regions, small proportion of fully/partially vaccinated participants, and small number of participants <18 years.

SAP Version (Approval Date)	Protocol Version (Date) on which SAP is Based	Change	Rationale
		
• Addition of Kaplan-Meier plot summarizing time to undetectable viral load• Addition of new subgroup and PK-PD analyses.	

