- Population: All participants in the Intent-to-Treat (ITT) analysis set excluding participants who did not meet key inclusion/exclusion criteria (see section 4.2.2.1).
- Endpoint: Progression of COVID-19 through Day 29 as defined by hospitalization > 24 hours for acute management of illness due to any cause or death
- Summary measure: Absolute difference in the proportion of participants meeting the primary endpoint
- The anticipated intercurrent events are:
 - Not receiving randomized treatment or an alternative study treatment (i.e. treatment misallocation)
 - Discontinuation of study intervention as described in Protocol Section 7.1.
 - Use of medication not permitted during the study as listed in Protocol Section 6.8.1 up to Day 29

All intercurrent events will be handled using a hypothetical strategy where data collected after the occurrence of an intercurrent event will be excluded from the analysis, i.e. assuming the intercurrent event had not occurred.

Rationale for estimand: A hypothetical estimand is used as this is considered more conservative than treatment policy and therefore more appropriate for a non-inferiority comparison.

Supplementary Estimand for the Primary Endpoint

A supplementary estimand will be conducted based on all participants in the ITT analysis set by handling all intercurrent events with a treatment policy strategy (i.e. regardless of the intercurrent events occurring), with all the other attributes being the same as in the primary estimand. To estimate this estimand, all data collected in the ITT analysis set up to Day 29 will be included in the analysis.

[figure not shown]
[figure not shown]
Estimands for Key Secondary Endpoints

The estimand for the secondary endpoint 'Mean area under the curve of SARS-CoV-2 viral load in nasal secretions as measured by qRT-PCR from Day 1 to Day 8 (AUC_{D1-8})' is described by the following attributes:

- Population: All participants in the Virology analysis set, as defined in Section 3
- Summary measure: Treatment ratio (IM/IV) of mean \log_{10} AUC_{D1-8}
- Intercurrent events: Death and use of medication not permitted during the study as listed in Protocol Section 6.8.1 up to day 8
 - Strategy for Death: Composite strategy, where for participants who die prior to Day 8, the AUC_{D1-8} viral load value will be imputed using the worst AUC_{D1-8} viral load value from other participants in the same treatment arm.

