2.1. Multiplicity Adjustment

Hypotheses (1) and (2) above will be tested using the primary estimand according to the hierarchical testing principal as follows:

- If the null hypothesis for (1) is rejected, i.e., the upper bound of the two-sided 95% confidence interval for the risk difference between sotrovimab 500 mg IM and

sotrovimab 500 mg IV is less than the pre-specified 3.5% non-inferiority margin, then hypothesis for (2) will be tested.

- If the null hypothesis for (1) is not rejected, then hypothesis for (2) will not be tested.

Below is a summary of possible outcomes of the hierarchical testing procedure:

Which Null Hypothesis is Rejected	Non-inferiority Declared For
Hypotheses (1) and (2)	Both sotrovimab 500 mg IM and sotrovimab 250 mg IM (vs. sotrovimab 500 mg IV)
Hypothesis (1) but Not (2)	Only sotrovimab 500 mg IM vs. sotrovimab 500 mg IV
Hypothesis (1) is NOT rejected (Null hypothesis for (2) won't be tested in this case)	Neither sotrovimab 500mg IM nor sotrovimab 250mg IM (vs sotrovimab 500mg IV)

Two secondary endpoints will be formally analysed:

- 1) Mean area under the curve of SARS-CoV-2 viral load in nasal secretions as measured by qRT-PCR from Day 1 to Day 8 (AUC_{D1-8}). Each IM dose will be assessed for equivalence to IV based on the two-sided 90% confidence interval for the treatment ratio falling within equivalence bounds of 0.5 to 2.0.
- 2) Progression of COVID-19 through Day 29 as defined by visit to a hospital emergency room for management of illness OR Hospitalization for acute management of illness for any duration and for any cause OR Death. Each IM dose will be assessed for non-inferiority vs IV using a non-inferiority margin of 3.5% on the risk difference scale.

The testing of the two secondary endpoints above is adjusted for multiplicity by using the following hierarchy:

- Secondary endpoint (1) will only be tested if non-inferiority is achieved for sotrovimab 500 mg IM vs. sotrovimab 500 mg IV and sotrovimab 250 mg IM vs. sotrovimab 500 mg IV comparisons for the primary endpoint.

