- Secondary endpoint (1) will be tested in the same sequential way as the primary endpoint i.e If the null hypothesis for sotrovimab 500 mg IM vs. sotrovimab 500 mg IV is rejected, then the null hypothesis for sotrovimab 250 mg IM vs. sotrovimab 500 mg IV will be tested. If the null hypothesis for sotrovimab 250 mg IM vs sotrovimab 500mg IV for secondary endpoint (1) is rejected, then secondary endpoint (2) will be tested in the same sequential manner as secondary endpoint (1).

Given that recruitment to the sotrovimab 250 mg IM arm was permanently discontinued following the *ad hoc* interim analysis on 11-Aug-2021, the sotrovimab 250 mg IM arm will not

be formally compared to the sotrovimab 500 mg IV arm. Therefore only hypotheses for primary and secondary endpoints related to the 500 mg IM arm will be formally tested in the above framework and hypotheses related to the 250 mg IM arm are removed from the testing hierarchy.

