4.1.3. Missing Data Handling Rules

- Missing data can occur due to study withdrawal or participants lost to follow-up before the completion of the study or due to intermittent missing values (i.e. data between two non-missing assessments).
- In addition, for the hypothetical estimands of the primary and secondary COVID-19 progression endpoints, data collected after the occurrence of an intercurrent event will be excluded from the analysis and will therefore be set to missing.
- For the primary and secondary COVID-19 progression endpoints, missing data will be imputed under a missing at random (MAR) assumption using a multiple imputation (MI) model. More details are provided in Section 6.2.8.

- For all other endpoints, a treatment policy strategy will be used for all intercurrent events where all data captured will be included in the summary and analysis, unless otherwise stated.

The following rules will be applied to viral load endpoints:

- The imputation logic when a sample is reported as 'NEG' (below lower-limit of detection) or '<2.08' (below lower-limit of quantification) is to impute as $0.5 \times 120 \text{ copies/ml} = 60 \text{ copies/ml} = 1.78 \log_{10} \text{ copies/ml}$
- Subjects who die prior to Day 8 (or Day 5 or Day 11), their AUC viral load value will be imputed using the worst AUC viral load value from other subjects in the same treatment arm who have completed Day 8 (5/11) and have a valid AUC(D1-8)/(D1-5)/(D1-11).
- If Day 8 assessment alone is missing but Day 5 and Day 11 assessments are available, the Day 8 will be imputed using linear interpolation between Day 5 and Day 11. AUC will be calculated then.
- If more than 2 consecutive assessments are missing prior to and including Day X, then the AUC(D1-X) will not be calculated.
- If a subject is lost to follow-up prior to Day X, then AUC(D1-X) will be set to missing.

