4.3.1.5. Reduction in SARS-CoV-2 Viral Load

Viral load will be \log_{10} -transformed prior to summary and analysis. The Virology analysis set will be used for all analyses.

Reduction of SARS-CoV-2 viral shedding will be determined by the change from baseline of SARS-CoV-2 nasal viral load at Day 8.

In addition, the SARS-CoV-2 viral load will also be assessed from the area under the curve (AUC as determined by the trapezoidal rule) of \log_{10} -transformed SARS-CoV-2 viral load through Days 1 to 8. AUC will be log-transformed prior to analysis.

The proportion of participants with a persistently high SARS-CoV-2 viral load (PHVL) assessed by qRT-PCR at Day 8 will also be assessed. PHVL is defined as a viral load value $>4.1 \log_{10}$ copies/ml at Day 8.

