4.3.2.2. Continuous Endpoints

The following secondary endpoints will be summarised/analysed as continuous endpoints:

- Change from baseline in viral load in nasal secretions by qRT-PCR at Day 8
- Area under the curve (AUC) of SARS-CoV-2 viral load as measured by qRT-PCR from Day 1 to Day 8 (AUC_{D1-8})
- Serum pharmacokinetic concentrations

Change from baseline in viral load at all visits including Day 8 will be summarised on the log10 scale. The Virology analysis set will be used.

AUC_{D1-8} for log10-transformed SARS-CoV-2 viral load will be analyzed using analysis of covariance adjusted for treatment group (sotrovimab 500mg IV, sotrovimab 500mg IM), baseline viral load, derived age group (<65 years old, ≥ 65 years old, see Section 6.2.7), and gender (female, male). AUC will be log-transformed prior to analysis. The treatment ratio and two-sided 90% CI for the comparison of sotrovimab 500mg IM vs sotrovimab 500mg IV will be calculated by back-transforming the corresponding estimates on the log-scale.

In addition, the following will be produced:

- Box plot of serum pharmacokinetic concentrations at Day 8, 15 and 29 vs COVID-19 progression status through Day 29 (as defined in section 4.2.1) for the hypothetical estimand, overall and by treatment group

- Summary table of Day 8 serum pharmacokinetic concentrations (n, mean, SD, median, min, max) by COVID-19 progression status through Day 29 (as defined in section 4.2.1) for the hypothetical estimand, total and by treatment group.

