4.4.1.7. Reduction in SARS-CoV-2 Viral Load

Viral load will be \log_{10} -transformed prior to summary and analysis. The Virology analysis set will be used for all analyses.

Reduction of SARS-CoV-2 viral shedding will be determined by the change from baseline of SARS-CoV-2 nasal viral load at Day 3, Day 5, Day 11, Day 15, Day 22, and Day 29.

In addition, the SARS-CoV-2 viral load will also be assessed from the area under the curve (AUC as determined by the trapezoidal rule) of \log_{10} -transformed SARS-CoV-2 viral load through Days 1 to 5 (AUC_{D1-5}) and Days 1 to 11 (AUC_{D1-11}). AUC will be log-transformed prior to analysis.

The proportion of participants with undetectable, unquantifiable and positive SARS-CoV-2 in nasal secretions by qRT-PCR at Day 3, Day 5, Day 8, Day 11, Day 15, Day 22, and Day 29 will be summarised.

In addition a Kaplan-Meier plot of time to undetectable SARS-CoV-2 in nasal secretions by qRT-PCR by treatment group will be produced. For the purposes on the plot, a confirmed negative PCR is defined as first of two or more consecutive negative (no SARS-CoV2 detected) PCR tests.

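### The 0.5 to 2.0 equivalence bounds for viral-load AUC apply to a ratio of areas under log10 values, so either bound corresponds to at least about a 60-fold difference in viral load

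*SAP*

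**What the plan says.** AUC from Day 1 to Day 8 is one of two formally analysed secondary endpoints in SAP section 2.1. Equivalence of IM to IV rests on the "two-sided 90% confidence interval for the treatment ratio falling within equivalence bounds of 0.5 to 2.0". After the 250 mg IM arm was dropped, the same section keeps the test for the remaining comparison: "only hypotheses for primary and secondary endpoints related to the 500 mg IM arm will be formally tested in the above framework".

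The derivation is in two places. Section 4.3.1.5 applies the trapezoidal rule to log10-transformed "SARS-CoV-2 viral load through Days 1 to 8. AUC will be log-transformed prior to analysis". Section 4.3.2.2 states that AUC "for log10-transformed SARS-CoV-2 viral load will be analyzed using analysis of covariance adjusted for treatment group", baseline viral load, age group and gender, again with AUC logged first. The ratio and its CI come from back-transforming the estimates on that log scale. Section 4.4.1.7 derives the exploratory AUCs (Days 1 to 5 and 1 to 11) in the same way.

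Section 4.1.3 fixes the lowest value that can enter the analysis. The rule for samples below detection or "below lower-limit of quantification) is to impute as" gives 0.5 × 120 = 60 copies/ml, or 1.78 log10.

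The estimand in section 1.1 is worded more loosely: "Summary measure: Treatment ratio (IM/IV) of mean" log10 AUC.

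**The concern.** Bounds of 0.5 to 2.0 are naturally read as IM viral load lying within two-fold of IV. They would mean that only if the AUC were on the copies scale. Here two logs are taken and one is undone, so the ratio compares average log10 values. Doubling an average log10 value squares the viral load.

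The label is formal, not descriptive. The Protocol synopsis (Rationale) reports that the primary comparison met its margin (upper limit 3.45% against 3.5%), so the testing sequence reaches this endpoint. If a pass is reported as virologic equivalence, readers will credit IM dosing with something the test cannot show. It would pass even an IM arm that had lost much of the antiviral effect.

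**Working it through.** **Inputs from the SAP.** Bounds 0.5 and 2.0 (2.1); trapezoid of log10 values, then log of AUC (4.3.1.5, 4.3.2.2); floor 1.78 log10 (4.1.3); Virology set restricted to a quantifiable Day 1 swab (3).

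**The plan's own figure.** log10(0.5 × 120) = log10(60) = 1.778, which rounds to the stated 1.78. log10(120) = 2.079, which rounds to the stated 2.08.

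**Minimum meaning of a bound.** Let m = AUC/7 be the time-averaged log10 load, summarised per arm by its geometric mean, as the model does. Every value is at least 1.78, so m ≥ 1.78 in both arms.
- Ratio 2.0: m_IM − m_IV = 2·m_IV − m_IV = m_IV ≥ 1.78.
- Ratio 0.5: m_IV − m_IM = m_IM ≥ 1.78.
- 10^1.78 ≈ 60-fold in either direction.

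The quantifiable baseline raises this slightly. The smallest possible AUC is (2.08 + 1.78) + 2 × 1.78 + 3 × 1.78 = 12.76, so m = 1.823, about 66-fold. At m = 4 (the lowest baseline viral-load cut-point in SAP 4.6.1) the bound means 10^4 = 10,000-fold.

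**Illustrations.** The documents give no viral-load results, so four IV curves are assumed (log10 copies/ml on Days 1, 3, 5, 8). Raising every post-baseline value by s adds s + 2s + 3s = 6s to the AUC, so the ratio is 1 + 6s/AUC. An arm with no decline has AUC 7 × baseline. An arm with half the decline has the mean of that and the IV AUC.

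| Assumed IV curve | AUC | IM 2-fold higher | 10-fold | 100-fold | 1,000-fold | Half the decline | No decline | s needed for 2.0 |
|---|---|---|---|---|---|---|---|---|
| 5, 4.2, 3.4, 2.5 | 25.65 | 1.07 | 1.23 | 1.47 | 1.70 | 1.18 | 1.37 | 4.3 |
| 6, 5.3, 4.5, 3.5 | 33.10 | 1.05 | 1.18 | 1.36 | 1.54 | 1.13 | 1.27 | 5.5 |
| 6.5, 5.6, 4.7, 3.6 | 34.85 | 1.05 | 1.17 | 1.34 | 1.52 | 1.15 | 1.31 | 5.8 |
| 7, 6.2, 5.2, 4.1 | 38.55 | 1.05 | 1.16 | 1.31 | 1.47 | 1.14 | 1.27 | 6.4 |

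Half the decline leaves Day 8 load 18- to 28-fold higher (10^1.25 to 10^1.45), yet the ratio stays below 1.2.

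**Simulation of the specified test.**
- Scenarios: four curves; IM arms 10-fold higher, 100-fold higher, half decline and no decline; 200 or 300 per arm; 500 trials per setting.
- Assumed SDs (baseline, slope, residual): 1.3/1.2/0.8 and 1.8/2.0/1.2 log10.
- Rules: participants with baseline below 2.08 excluded; later values below 2.08 set to 1.78.
- Model: ANCOVA of log AUC on treatment and baseline (age and gender not simulated).
- Result: the residual SD of log AUC was 0.16 to 0.28, and all 4 × 4 × 2 × 2 × 500 = 32,000 trials declared equivalence.

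**The other reading of section 1.1.** If the AUC were on the copies scale, a 2-fold higher IM load would give 1.23 to 1.33 on these curves. The ratio would reach 2.0 at 4.1- to 5.4-fold, because both arms share the Day 1 value.

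**The case against.** Several points can be made for the plan.

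- **The curves clear slowly.** All four assumed curves stay above 2.08 log10 at Day 8. With very fast IV clearance the ratio discriminates better: IV at 6, 1.78, 1.78, 1.78 against no IM decline gives 42/16.68 = 2.52. With mean IV values 6, 3, 1, 0 before flooring and 200 per arm, a no-decline arm passed in 67% of simulated trials with the larger SDs and in 0% with the smaller. This stands: the 100% pass rate for no decline holds only for slower clearance. The 10-fold, 100-fold and half-decline arms still passed every time under the fast-clearing curves, so the point about partial loss of effect is unchanged.
- **The 60-fold minimum is not strict.** The model compares geometric means of individual AUCs, and very unequal spread between arms can lower the equivalent gap. One constructed example gives 1.73 log10, about 54-fold; an extreme one gives about 40-fold. This is correct but does not rescue the bounds.
- **A CI close to 1 would be informative.** It would, because of its width and not because it lies inside 0.5 to 2.0. That argues for reporting the difference in log10 units.
- **Other virology is reported.** Change from baseline, persistently high load, undetectable proportions and a Kaplan-Meier plot are planned, but as summaries without a test. They do not correct a formal equivalence label.
- **A rationale may sit elsewhere.** The SAP is based on Protocol Amendment 3, which was not available for review, so the absence of a rationale is not held against the plan. Any rationale would still have to defend a bound of roughly 60-fold or more.

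**Conclusion.** The concern holds and should be fixed in reporting. On the derivation stated in three SAP sections, each bound means a difference in time-averaged viral load of at least about 60-fold, and 10,000-fold if the lower arm averages 4 log10. The 60-fold figure rests only on the SAP's floor and on similar spread within arms; the table and simulation rest on assumed curves and SDs. Meeting 0.5 to 2.0 cannot by itself support virologic equivalence.

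The damage is limited. The primary non-inferiority test, the type I error of the second formal secondary endpoint and the Amendment 4 safety substudy (descriptive, with no AUC endpoint) are unaffected. An IM arm with no antiviral effect would also seldom have passed the primary test that precedes this one.

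**What to change.** 1. Report the pre-specified ratio and its 90% CI as run, so that the sequence to the second formal secondary endpoint is unchanged. State beside it what the ratio means in fold differences, and make no equivalence claim from it.
2. Align the estimand wording in SAP 1.1 with 4.3.1.5 and 4.3.2.2.
3. Add a supplementary ANCOVA of time-averaged log10 viral load (AUC divided by 7, no second log) with the same covariates. Report the IM minus IV difference in log10 units, its antilog and the 90% CI.
4. Any equivalence limits on that scale need the sponsor's justification and must be labelled post hoc, since Day 29 results are already reported.

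The cost is one derived variable, one model and report wording, with no new data. The formal equivalence claim is lost.

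Precision is adequate for description. With a residual SD of 0.83 to 1.38 log10 (simulation range, assumed inputs), the half-width is 1.645 × SD × √(2/n): 0.11 to 0.19 log10 at 300 per arm (1.3- to 1.5-fold) and 0.14 to 0.23 at 200 per arm (1.4- to 1.7-fold). The half-decline arm differs by 0.53 to 0.73 log10 on this scale in the simulation, so it would be plainly visible.

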3. ANALYSIS SETS

Analysis Set	Definition / Criteria	Analyses Evaluated
Screened	All participants who were screened for eligibility	Study Population
Enrolled	All participants who entered the study Note screening failures (who never passed screening even if rescreened) are excluded from the Enrolled analysis set as they did not enter the study	Study Population
Randomized	All participants who were randomized. Participants will be analyzed according to the route of administration and dose level they were randomized to: sotrovimab IM (500 mg), sotrovimab IM (250 mg) or sotrovimab IV (500 mg).	Study Population
Intent-to-Treat (ITT)	All participants who were randomized. Participants who were randomized under Protocol Amendment Version 1 and were immunocompetent and fully vaccinated at randomisation will be excluded. Participants will be analyzed according to the route of administration and dose level they were randomized to: sotrovimab IM (500 mg), sotrovimab IM (250 mg) or sotrovimab IV (500 mg).	Study Population Efficacy
Safety	All randomized participants who are exposed to study intervention. Participants will be analyzed according to the route of administration and dose level they actually received: sotrovimab IM (500 mg), sotrovimab IM (250 mg) or sotrovimab IV (500 mg).	Study Population Safety
Pharmacokinetic (PK)	All participants in the Safety analysis set who had at least 1 non-missing PK assessment (Non-quantifiable [NQ] values will be considered as non-missing values). Participants will be analyzed according to the route of administration and dose level they actually received.	PK

Analysis Set	Definition / Criteria	Analyses Evaluated
Virology	
All participants in the ITT analysis set with a lab confirmed quantifiable baseline nasopharyngeal swab at Day 1.
 
Participants will be analyzed according to the route of administration and dose level they were randomized to: sotrovimab IM (500 mg), sotrovimab IM (250 mg) or sotrovimab IV (500 mg).
 
This will be the primary analysis set for virology.
	Efficacy (Virology)

4. STATISTICAL ANALYSES

4.1. General Considerations

4.1.1. General Methodology

The ITT Analysis Set will be used for all Study Population analyses and Efficacy analyses, unless otherwise specified. A subset of the ITT analysis set will be used for the primary estimand, excluding participants who did not meet key inclusion/exclusion criteria (see 4.2.2). The Safety Analysis Set will be used for selected Study Population summaries and all safety analyses. The PK analysis Set will be used for all PK analyses. Virology analysis set will be used for all Virology analyses.

In the case of a difference between the stratification assigned at the time of randomization and the data collected in the eCRF, the analyses will be performed based on the data collected in the eCRF, not the assigned stratum at randomization. All analyses will be adjusted for treatment group (sotrovimab 500mg IV, sotrovimab 500mg IM), derived age group (<65 years old, ≥65 years old, see Section 6.2.7), and gender (female, male). Stratification factors of region and vaccination status are not included as covariates due to the small number of non-US and partially/fully vaccinated participants in the ITT analysis set. In addition the 12-17 years old and 18-64 years old categories are combined due to the small number of participants in the 12-17 years old category.

In the case of model convergence issues, if one category dominates within a particular covariate then that covariate may be considered for removal from the model.

Confidence intervals will use two-sided 95% confidence levels unless otherwise specified.

Unless otherwise specified, continuous data will be summarized using descriptive statistics: n, mean, standard deviation (std), median, minimum and maximum. For log-transformed data (e.g. AUC) descriptive statistics will present the geometric mean, standard deviation (SD of log-transformed data) and coefficient of variation. Categorical data will be summarized as the number and percentage of participants in each category.

Efficacy data will be reported according to nominal time of clinical visits unless otherwise stated. Hospitalization status, oxygen supplementation and healthcare resource utilization use will be slotted against the clinical visit date for summaries and analyses by visit.

All data will be reported according to the nominal time of clinic visits and assessments as specified in the protocol unless stated otherwise:

- Day 8, Day 11, Day 15, Day 22, where data within ± 1 days of the target day may be used if data is not recorded on the actual day
- Day 29, where data within ± 2 days of the target day may be used if data is not recorded on the actual day
- Day 57, where data within ± 4 days of the target day may be used if data is not recorded on the actual day
- Day 85, Day 113, Day 141, Day 169, Day 197, Day 224, Day 252 where data within ± 7 days of the target day may be used if data is not recorded on the actual day

It is anticipated that patient accrual will be spread thinly across centers and summaries of data by center would unlikely be informative and will not, therefore, be provided.

